# 1. GLOSSARY OF ABBREVIATIONS

AE	adverse event
ALT	alanine aminotransferase
AST	aspartate aminotransferase
AUC	area under the curve
BCX-1812	Peramivir
BUN	blood urea nitrogen
CI	confidence interval
CRF	case report form
DAIDS	Division of Acquired Immunodeficiency Syndrome, National Institute of Allergy and Infectious Diseases, National Institutes of Health
FDA	Food and Drug Administration
HGB	hemoglobin
IRC	influenza-related complications
ITT	intent-to-treat
ITTI	intent-to-treat infected
MedDRA	Medical Dictionary for Regulatory Activities
PCR	polymerase chain reaction
PK	Pharmacokinetic
RAT	rapid antigen test
SD	standard deviation
TCID 50	Tissue-culture infective dose 50
TEAEs	treatment-emergent adverse events
TWAUC	time-weighted area under the curve
WHO	World Health Organization

# 2. INTRODUCTION

This document describes the statistical methods and data presentations to be used in the summary and analysis of data from Protocol BCX1812-305. Background information is provided for the overall study design and objectives. The reader is referred to the study protocol and case report forms (CRFs) for details of study conduct and data collection.

This document describes all analyses of safety, clinical effectiveness, pharmacokinetics and virology analyses. Pharmacokinetic and virology analyses will be written as separate reports from the clinical study report.

#### 2.1. STUDY OVERVIEW

Protocol BCX1812-305 is a multicenter, randomized, open-label, active-controlled study to evaluate the safety, pharmacokinetics and effectiveness of a single dose of intravenous (IV) peramivir (600 mg IV or 12 mg/kg IV depending on age) compared to oral oseltamivir (dosed BID for 5 days) in children with uncomplicated acute influenza. Approximately 140 subjects will be enrolled. Up to 10 subjects ages from birth to <– 28- days will be enrolled and will receive a single dose of intravenous (IV) peramivir 12 mg/kg. Up to 20 subjects 28 days to less than 2 years old will be enrolled. Subjects enrolled in this cohort prior to version 4.0 of the protocol will be randomized 4:1 (4 IV peramivir: 1 oral oseltamivir) whereas subjects enrolling in this cohort under version 4.0 or higher of the protocol will receive IV peramivir 12mg/kg. Up to 110 subjects 2 years to < 18 years of age will be randomized 4:1 (4 IV peramivir: 1 oral oseltamivir) according to the following age groups:

- 2 years < 7 years: up to 40 subjects
- 7 years < 13 years: up to 40 subjects
- 13 years < 18 years: up to 30 subjects

Eligible subjects with have clinical signs and symptoms consistent with acute influenza infection consisting of an oral temperature  $\geq 100^{\circ}F$  or rectal temperature  $\geq 101.3^{\circ}F$  with at least one respiratory symptom (cough or rhinitis) OR a positive influenza rapid antigen test (RAT). Enrollment of eligible subjects based on clinical symptoms alone will be approved by the Sponsor at the beginning of each influenza season.

The formulation of the peramivir drug to be used in this study contains peramivir at a concentration of 10 mg/mL. The peramivir 10 mg/mL stock solution will be diluted in saline using aseptic techniques with a maximum volume of 100 mL. Oseltamivir will be prepared and administered in accordance with the manufacturer's instructions.

Subjects will record temperature, influenza symptoms, date and time of oral oseltamivir dose administration (if applicable), the ability to return to day care/school and/or resume their normal daily activities, appetite and eating patterns, and doses of symptomatic relief medication in a Subject Diary. Temperature measurements will be taken every 12 hours until temperature

normalizes for 48 hours (i.e., temperature without antipyretic is < 99.4 orally in children  $\geq$  6 and < 98.4 axillary in children < 6 years old for 4 measurements). Subjects 7 years of age and older will have the following 7 influenza symptoms recorded using a 4-point severity scale twice daily beginning pre-dose on Day 1 assessment until symptom resolution and through the last follow-up visit (whichever comes first): cough, sore throat, nasal obstruction, myalgia, headache, feverishness, and fatigue. Subjects  $\geq$  4 and  $\leq$  6 years of age will have the following 7 influenza symptoms recorded using a 4-point severity scale twice daily beginning pre-dose on Day 1 assessment until symptom resolution and through the last follow-up visit (whichever comes first): cough, sore throat, nasal obstruction, myalgia, headache, feverishness, fatigue/malaise, and gastrointestinal symptoms (nausea, vomiting, or diarrhea). Subjects 28 days to < 4 years old will have the following 5 influenza symptoms recorded using a 4-point severity scale twice daily beginning pre-dose on Day 1 assessment until symptom resolution and through the last follow-up visit (whichever comes first): cough, rhinitis, feverishness, malaise/irritability, and gastrointestinal symptoms (nausea, vomiting, or diarrhea).

Subjects will undergo follow-up assessments on Days 3, 7, and 14. The Day 3 visit may be a home visit (performed by a qualified study nurse). Day 7 is required to take place in the clinic, and Day 14 may either be a clinic visit, home visit, or follow-up phone call to the subject/parent/guardian.

An adequate nasal swab specimen will be collected from all enrolled subjects on Day 1 prior to dosing and at the follow-up assessments on study Days 3, 7, and 14 for virus sub-type identification and quantitative virologic assessments. Specimens from all subjects yielding influenza virus will also be assessed for susceptibility to neuraminidase inhibitors (Day 1 and last specimen yielding influenza virus on culture).

Plasma samples for determination of drug concentration on subjects randomized to peramivir will be drawn as follows:

Up to 4 blood samples will be drawn, where possible, during the following time periods, beginning from the end of dosing until release from the site:

- One time point immediately following completion of the infusion
- One time point from 30 minutes to 1 hour post-infusion
- One time point from 1 hour to 3 hours post-infusion
- One time point from 3 hours to 6 hours post-infusion

Adverse events, physical examinations, laboratory tests, concomitant medications, and vital signs will be used to monitor subject safety, while daily subject-rated assessments of influenza symptoms and viral titers will be measured to determine effectiveness. The primary safety endpoints include the incidence of treatment-emergent adverse events and treatment-emergent changes in clinical laboratory test. The secondary effectiveness endpoints include the time to alleviation of clinical symptoms of influenza (per age appropriate symptoms), defined as the start of the time period when all of the symptoms assessed are either absent or are present at no more than mild severity level and at this status for a 21.5 hour (24 hours - 10%) period, time to resolution of fever, change

in influenza virus titer by  $\log_{10}$  tissue culture infective  $dose_{50}/mL$  (TCID50), and change in viral sensitivity.

# 2.2. SCHEDULE OF EVENTS/STUDY VISITS

Assessments	Screening 	Baseline  Pre-Dose	Day 1  Post-Dose	Day 3 	Day 7 (±2 day)	Day 14  (±3 day)	End of Study Early Withdrawal 
Informed Consent	X						
Inclusion/Exclusion Criteria	X						
Pregnancy Test (Urine) 	X				X		X
Medical History	X						
Body Temperature 	X	X	X	X	X	X	X
Physical Exam		X					
Influenza-related complications (IRC) checklist 		X		X	X	X	X
Vital Signs 		X		X	X	X	X
Concomitant Medications Review 	X	X	X	X	X	X	X
Clinical Chemistries and Hematology 		X			X		X
Urinalysis 		X			X		X
Assessment of influenza symptoms/ activities of daily living/ eating habits 		X	X	X	X	X	X
Subject Diary Completion/ Review 		X	X	X	X	X	X
Nasal swabs for Virology Analysis 		X		X	X	X	X
Study Drug Administration 		X					
Serum sample for influenza antibody analysis 		X			X		
Pharmacokinetic (PK) Sampling 			X				
Adverse Events			X	X	X	X 	$X^{16}$

Study Measurements and Visit Schedule Figure Legend on Next Page

# Study Measurements and Visit Schedule Figure Legend

It is expected that the date of Screening, Baseline, and Day 1 (date of administration of study drug) will be the same.

-  The Day 3 visit may be performed as a clinic visit or home visit (conducted by a qualified study nurse). The Day 14 visit may be performed as a home visit, clinic visit, or phone call. In the event the Day 14 assessment is a phone call the parent/caregiver will be requested to mail the completed diary card back to the site.
- An Early Withdrawal assessment should be conducted for subjects who withdraw before Day 7. For subjects who withdraw between Day 7 and Day 14 a telephone assessment should be completed, where possible.
-  Urine pregnancy test will be performed for any female post-menarche.
-  The screening temperature may be performed per the site's standard method, which will be recorded. For subsequent visits, the parent/guardian will record oral or axillary temperature with the electronic thermometer provided by BioCryst. Thereafter, the parent/caregiver will record temperature in the Subject Diary approximately every 12 hours until temperature is normal for 48 hours without antipyretic.
-  If an IRC is suspected then a targeted physical examination and if needed, diagnostic testing will be conducted to record the actual presence/absence of the IRC.
-  Vital sign measures will include blood pressure (in children <2 only if clinically indicated), pulse rate and respiration rate. Vital signs will be recorded at Baseline, and vital signs will be taken once on remaining study visits.
-  Antipyretic medications will be recorded in the Subject Diary by the parent/caregiver daily from Day 1 through Day 14.
-  Clinical laboratory assessments performed at Baseline (by a local lab) are for the purpose of establishing a baseline. Subject may be enrolled and begin treatment with study drug prior to receiving results.
-  The severity of age appropriate influenza signs and symptoms will be recorded by the parent/caregiver in the Subject Diary twice daily, until all symptoms are resolved (Grade 0). Assessments of activities of daily living and eating habits will be recorded once daily until all symptoms are resolved.
- On Day 1, the parents/caregivers of subjects and/or adolescent subjects are to be provided training by the study staff on completing the Subject Diary. Instructions will be reviewed with the adolescent subject or parent/caregiver at each study visit.
-  Swabs for virology analysis will be collected on Day 14 where possible.
- Only for those subject randomized to peramivir. The parents/caregivers of subject randomized to the oral oseltamivir arm of the study, will record the date and time of each drug administration, from Day 1 until Day 5 (or last scheduled dose). The first dosing will be administered at the site and documented by the study staff following completion of required predose activities.
-  A single serum specimen will be collected, where possible, pre-dose on Day 1 and on Day 7 for analysis of influenza antibody titers. .
- Only for those subjects randomized to peramivir. A PK sample will be drawn immediately following the end of study drug infusion/administration, between 30 minutes to 1 hour post-infusion, between 1 and 3 hours post-infusion, and between 3 and 6 hours post-infusion.
- Any subject with unresolved moderate or severe intensity influenza symptoms or an unresolved AE and/or treatment-emergent laboratory finding that requires further medical management may be evaluated in further follow-up visits, at the Investigator's discretion.

# 3. OBJECTIVES

The primary objective of the study is to evaluate the safety of IV peramivir compared to oral oseltamivir in pediatric subjects with acute uncomplicated influenza.

The following secondary objectives are planned for this study.

- To describe the pharmacokinetics of IV peramivir in pediatric subjects with influenza.
- To evaluate the effectiveness of IV peramivir compared to oral oseltamivir in pediatric subjects with influenza.
- To evaluate the incidence of influenza complications, specifically otitis media, sinusitis, bronchitis or pneumonia requiring antibiotic use diagnosed after initiation of treatment.

# 4. GENERAL STATISTICAL CONSIDERATIONS

#### 4.1. SAMPLE SIZE AND POWER

The study is designed to evaluate the safety and pharmacokinetics of IV administration of peramivir in pediatric subjects with influenza. A formal sample size calculation was not performed.

#### 4.2. RANDOMIZATION AND MASKING

Approximately 140 subjects will be enrolled. Up to 10 subjects from birth to < 28 days will be enrolled to receive a single dose of IV peramivir. Up to 20 subjects from 28 days to < 2 years will either be randomized to 1 of 2 treatment arms at a ratio of 4:1 or will receive a single dose of IV peramivir. Up to 110 subjects from 28-days to < 18 years of age will be randomized to 1 of 2 treatment arms at a ratio of 4:1:

- Treatment Group 1: A single dose of IV peramivir
- Treatment Group 2: Oral oseltamivir given BID for 5 days

This is an open label study and as such, blinding is not applicable.

#### 4.3. HANDLING OF DATA

#### 4.3.1. Strata and Covariates

Analyses will be presented by the stratification factor of age group at randomization.

# 4.3.2. Examination of Subject Subsets

Some analyses will be displayed by viral subtype at Screening.

# 4.3.3. Multiple Testing and Comparisons

All analyses will be conducted without adjustments for multiple testing.

#### 4.3.4. Missing Data and Outliers

Every effort will be made to obtain required data at each scheduled evaluation from all subjects who have been randomized. No attempt will be made retrospectively to obtain missing subject reported data (such as influenza symptom severity assessments, temperature, and injection site discomfort) that has not been completed by the subject at the time of return of the subject diary to the investigative site. In situations where it is not possible to obtain all data, it may be necessary to impute missing data, as described in the following paragraph.

In assessing the effectiveness endpoint of time to alleviation of symptoms, for subjects who withdraw or who do not experience alleviation of symptoms, missing data will be censored using the date of subject's last non-missing assessment of influenza symptoms. Missing assessments of influenza symptoms will be imputed using the last observation carried forward. For the subject diary data, the following data conventions will be utilized. Missing diary completion times will be imputed as 11:59 for diary entries designated as morning and 23:59 for evening and daily reported values. Entries with values exceeding the 24-hour clock will be handled on a case-by-case basis and reviewed by a member of the clinical project team prior to implementation. In general, values recorded between 24:01 – 24:59 will be interpreted as values past midnight and will be implemented as such. Values recorded as 60:00, 70:00, and 80:00 will be interpreted as 06:00, 07:00, and 08:00, respectively. Should additional data conventions be required, these will be documented in the derived variable specifications and in the final clinical study report. Select exploratory sensitivity analyses may be conducted to ascertain the effect, if any, of these methods. These sensitivity analyses are further described in section 6.2.2.1. Other secondary effectiveness endpoints with time to event data will be censored using the date of subject's last non-missing assessment of the given endpoint.

Unless otherwise specified, no other missing data will be imputed.

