- 7 Vital sign measures will include blood pressure (in children <2 only if clinically indicated), pulse rate, and respiration rate. Vital signs will be recorded at Baseline, and vital signs will be taken once on remaining study visit days.
- 8 Antipyretic medications will be recorded in the Subject Diary by the parent/caregiver daily from Day 1 through Day 14.
- 9 Clinical laboratory assessments performed at Baseline are for the purpose of establishing a baseline. Subjects may be enrolled and begin treatment with study drug prior to receiving results.
- 10 The severity of age appropriate influenza signs and symptoms will be recorded by the parent/caregiver in the Subject Diary twice daily, until all symptoms are resolved (Grade 0). Assessments of activities of daily living and eating habits will be recorded once daily until all symptoms are resolved.
- 11 On Day 1, the parents/caregivers of subjects and/or adolescent subjects are to be provided training by the study staff on completing the Subject Diary. Instructions will be reviewed with the adolescent subject or parent/caregiver at each study visit.
- 12 Swabs for virology analysis will be collected on Day 14 where possible.
- 13 Only for those subjects randomized to peramivir. The parents/caregivers of subjects randomized to the oral oseltamivir arm of the study, will record the date and time of each drug administration, from Day 1 until Day 5 (or last scheduled dose). The first dosing will be administered at the site and documented by the study staff following completion of required predose activities.
- 14 A single serum specimen will be collected, where possible, pre-dose on Day 1 and on Day 7 for analysis of influenza antibody titers. Subjects whose weight is < 10kg do not require a serum antibody sample.
- 15 Only for those subjects randomized to peramivir. A PK sample will be drawn immediately following the end of study drug infusion/administration, between 30 minutes to 1 hour post-infusion, between 1 and 3 hours post-infusion, and between 3 and 6 hours post-infusion. Note: Subjects ≥ 5 kg will have four 1.0 mL blood draws at the above stated sampling times. Subjects < 5 kg will have two 1.0 mL blood samples; one time immediately following completion of the infusion and one time between 1-3 hours post-infusion.

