13.8.2. Effectiveness Analyses

Time to resolution of fever, defined as a temperature < 99.4 oral or < 98.4 axillary with no antipyretic medications taken for at least 12 hours, will be estimated for each age group and overall by treatment group using the method of Kaplan-Meier. Subjects who do not achieve resolution of fever will be censored at the time of their last assessment.

Time to resolution of influenza symptoms, defined as the time from initiation of study drug until the start of the 21.5-hour period (24 hours- 10%) where all symptoms of influenza are recorded as none or mild, will be estimated for each age group and treatment group using the method of Kaplan-Meier. Subjects who do not experience alleviation of symptoms will be censored at the time of the last non-missing symptom assessment. As the number and type of symptoms varies by age, the analysis of time to resolution of symptoms will not be presented as an overall assessment.

Reduction in viral shedding will be assessed as the change from baseline in log₁₀ TCID₅₀/mL and RT-PCR, and will be summarized for each age group, treatment group and study visit.

Changes in virus susceptibility to neuraminidase inhibitors between virus cultured at Baseline and the last post-treatment sample from which virus can be cultured will be assessed using virology laboratory tests. Virology laboratory tests will include phenotypic characterizations of influenza virus recovered (hemagglutinin and neuraminidase) and viral susceptibility to peramivir, and genotypic analysis of primary virus isolates. These analyses will be presented separately by age group and viral subtype.

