# **6.2.2.** Effectiveness Analyses

A subject's oral temperature will be summarized by age group and overall by study visit and treatment group. A subject has Resolution of Fever if he/she has an oral temperature <99.4°F oral or <98.4°F axillary and no antipyretic medications have been taken for at least 12 hours. The time to resolution of fever will be estimated for each age group and overall by treatment group using the method of Kaplan-Meier using temperature and symptom relief medication information obtained from the subject diary data. Subjects who do not have resolution of fever will be censored at the time of their last non-missing post-baseline temperature assessment.

Alleviation of symptoms will be determined by assessment of symptoms as reported on each Subject Diary. The time to alleviation of symptoms will be estimated overall and for individual symptoms for each age group by treatment group using the method of Kaplan-Meier. Subjects who do not experience alleviation of symptoms will be censored at the date of their last non-missing post-baseline assessment.

Change from baseline in  $TCID_{50}/mL$  through Day 3, Day 7 and Day 14 respectively will be presented by age group and overall by treatment group for subjects with positive viral titers at baseline ( $log_{10} \ TCID_{50}/mL > 0.5$ ). A box plot and a histogram of the  $TCID_{50}/mL$  values will be presented by visit, age group, and treatment group. In addition, the median change from baseline in  $TCID_{50}/mL$  will be presented by visit, age group, and treatment group.

The number and percent of subjects with positive viral titers at baseline ( $log_{10} TCID_{50}/mL > 0.5$ ) that are shedding virus at each visit will be presented by age group and overall by treatment group.

The RT-PCR results at each visit will be presented by age group and overall by treatment group for subjects with positive RT-PCR results at baseline.

Change from baseline to last positive value of influenza virus susceptibility to neuraminidase inhibitors will be assessed using virology laboratory tests. Virology laboratory tests will include phenotypic characterizations of influenza virus recovered (hemaglutinin and neuraminidase) and viral susceptibility to zanamivir, oseltamivir, and peramivir, as well as genotyping of virus isolates. These analyses will be presented overall and by age group, treatment group and viral subtype.

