# 10. PROPOSED TABLES, LISTINGS, AND FIGURES FOR FINAL ANALYSIS

Output Number	Output Title
Table 14.1.1	Subject Follow-Up and Termination from Study; Intent-to-Treat Population
Table 14.1.2.1	Randomization, Eligibility, and Treatment Status; Intent-to-Treat Population
Figure 14.1.2.2	BCX1812-305 Study Population Disposition; Intent-to-Treat Population
Table 14.1.3	Demographics and Baseline Characteristics; Intent-to-Treat Population
Table 14.1.4	Populations for Analysis; Intent-to-Treat Population
Table 14.1.5	Summary of Subject Diary Completion; Intent-to-Treat-Infected Population
Table 14.2.1.1	Summary of Oral Temperature; Intent-to-Treat Infected Population
Table 14.2.1.2.1.1	Time to Resolution of Fever; Intent-to-Treat Infected Population
Figure 14.2.1.2.1.2	Time to Resolution of Fever (Kaplan-Meier Plot); ITTI Population
Figure 14.2.1.2.1.3	Median (95% CI) Time to Resolution of Fever; ITTI Population
Table 14.2.1.2.2	Time to Resolution of Fever by Viral Sub-Type; Intent-to-Treat Infected Population
Table 14.2.2.1.1.1	Time to Alleviation of Symptoms [1]; Intent-to-Treat Infected Population
Figure 14.2.2.1.1.2	Time to Alleviation of Symptoms (Kaplan-Meier Plot); ITTI Population
Figure 14.2.2.1.1.3	Median (95% CI) Time to Alleviation of Symptoms; ITTI Population
Table 14.2.2.1.2.1	Time to Alleviation of Symptoms [1] by Viral Sub-Type; Missing Values are Censored at the Last Available Assessment; Intent-to-Treat Infected Population

Output Number	Output Title
Figure 14.2.2.1.2.2	Median (95% CI) Time to Alleviation of Symptoms by Viral Sub- Type; ITTI Population
Table 14.2.3.1.1.1	Summary of Changes $\log_{10}$ Tissue Culture Infective Dose 50 (TCID 50 /mL) by Study Visit; Intent-to-Treat Infected Population
Figure 14.2.3.1.1.2	Box Plots of Viral Titers ( $TCID_{50}$ /mL) by Study Visit; Subjects with Negative Baseline Viral Titers are Excluded; Intent-to-Treat Infected Population
Figure 14.2.3.1.1.3	Histograms of Viral Titers ( $TCID_{50}$ /mL) by Study Visit; Subjects with Negative Baseline Viral Titers are Excluded; Intent-to-Treat Infected Population
Figure 14.2.3.1.1.4	Median (with IQR) Change from Baseline Viral Titers (TCID 50 /mL) by Study Visit; Subjects with Negative Baseline Viral Titers are Excluded; Intent-to-Treat Infected Population

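### SAP 4.3.4 does not say whether LOCF or censoring governs symptom ratings missing after a child's last entry, so alleviation status depends on the reading

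*SAP*

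**What the plan says.** SAP 4.3.4 gives two rules in consecutive sentences. For subjects who withdraw or do not alleviate, "missing data will be censored using the date of subject's last non-missing assessment of influenza symptoms". Then: "Missing assessments of influenza symptoms will be imputed using the last observation carried forward". The second sentence sets no maximum gap and does not require a later observed rating. Neither sentence says which is applied first.

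Elsewhere only censoring appears. SAP 6.2.2: "Subjects who do not experience alleviation of symptoms will be censored at the date of their last non-missing post-baseline assessment". Protocol 13.8.2: "Subjects who do not experience alleviation of symptoms will be censored at the time of the last non-missing symptom assessment". Protocol 13.7.4 also censors, and leaves further detail to the SAP.

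In the SAP section 10 output list, the title of subtype Table 14.2.2.1.2.1 includes "Missing Values are Censored at the Last Available Assessment". The title of the main Table 14.2.2.1.1.1 names no rule. Both titles carry a footnote [1] whose text is not given.

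The event (SAP 4.3.8, Protocol 13.8.2) requires every symptom to be none or mild for 21.5 h. Under note 10 to Protocol Table 1, symptoms are recorded "twice daily, until all symptoms are resolved (Grade 0"). On sensitivity analyses, SAP 4.3.4 says they may be conducted and adds: "These sensitivity analyses are further described in section 6.2.2.1". The SAP contents and text contain no section 6.2.2.1.

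**The concern.** With ratings about 12 h apart, 21.5 h at none or mild takes three consecutive ratings. A diary can end with only one or two. Carrying the last rating forward without limit then completes the 21.5 h and makes the child an event; censoring at the last rating does not.

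The diary instruction itself can produce this ending. A child who goes from moderate to all-absent within 12 h may stop recording, as told, before 21.5 h has been observed. That child has plausibly recovered. A child who withdraws after one mild rating has not been shown to recover. Unlimited carrying forward makes both of them events, and censoring alone makes neither an event.

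Time to alleviation is a listed secondary endpoint, summarized by Kaplan-Meier within age group and treatment. The oseltamivir arm is small: 140 planned minus about 117 on peramivir leaves about 23, split by age. One or two reclassified children can move a median in such cells. SAP section 6 requires independent programming, but where two programmers read 4.3.4 differently, the text does not say which of them is right.

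**Working it through.** The plan has no figure of its own to reproduce here, so the check has two parts.

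**1. Hypothetical diaries.** Inputs: ratings every 12 h from hour 0; the entry is the worst symptom grade; a dot is a missing rating; an event is grade 0 or 1 throughout at least 21.5 h, dated from the start of the spell. A missing rating that is not imputed breaks the spell.

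| Diary | LOCF everywhere | LOCF only between observed ratings | No imputation |
|---|---|---|---|
| 3,3,2,1,.,.,.,. | event 36 h | censored 36 h | censored 36 h |
| 3,2,1,1,.,.,.,. | event 24 h | censored 36 h | censored 36 h |
| 3,2,2,0,.,.,.,. (stopped at Grade 0) | event 36 h | censored 36 h | censored 36 h |
| 3,2,1,.,1,2,2,2 | event 24 h | event 24 h | censored 84 h |
| 3,2,1,.,1,1,1,0 | event 24 h | event 24 h | event 48 h |
| 3,3,2,2,.,.,.,. | censored 36 h | censored 36 h | censored 36 h |
| 3,3,2,1,1,1,0,0 | event 36 h | event 36 h | event 36 h |

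Status depends on the rule in the first three rows (short none/mild endings) and in the fourth (a gap followed by relapse). In the fifth row only the event time changes. Complete diaries and diaries ending at moderate are unaffected. (24 h less 10% is 21.6 h, not 21.5 h; with 12-hourly ratings no row changes.)

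**2. Illustrative size.** Assumptions, none of them from a rate in the documents: exponential times with median 30.5 h (the all-symptom median of the Japanese pediatric study in Protocol 5.3.2.1), and a share s of diaries ending 12 h into the none/mild spell. Then λ = ln 2 / 30.5 = 0.02273 per hour, e^(−12λ) = 0.7613 and e^(12λ) = 1.3135.

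Unlimited LOCF makes every affected child an event at the true time, so the median stays 30.5 h.

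If affected children are censored at the true time plus 12 h:
- cumulative hazard at 12 h: A = −ln[(1−s)·0.7613 + s]
- hazard after 12 h: h = (1−s)λ / [(1−s) + 1.3135s]
- median = 12 + (0.6931 − A)/h

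| s | A | h | Median | Change |
|---|---|---|---|---|
| 5% | 0.2572 | 0.02126 | 32.5 h | +7% |
| 10% | 0.2418 | 0.01983 | 34.8 h | +14% |
| 20% | 0.2119 | 0.01711 | 40.1 h | +32% |

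Now add visit ratings, taken as none/mild, with gaps between observed ratings filled.
- Day 3 only (48 h): an affected child becomes an event if 48 − T ≥ 21.5, that is T ≤ 26.5 h. Nobody is censored before 48 h, so the median solves (1−s)S(t) + s·S(26.5) = 0.5, with S(26.5) = e^(−26.5λ) = 0.5476. For s = 5%, 10% and 20%, S(t) = 0.4975, 0.4947 and 0.4881, giving 30.7, 31.0 and 31.6 h.
- Day 3 and Day 7 (144 h): every affected child with T ≤ 122.5 h becomes an event at T, so the median returns to 30.5 h for all three shares.

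**The case against.** The strongest reply is that the two sentences cover different things: LOCF fills missed ratings, and censoring applies to subjects who still have no event. Read that way they do not contradict each other, and a reader who infers a flat contradiction goes too far. What remains is that this reading does not fix the boundary. Imputing first and then censoring makes an event of a child who withdraws after one mild rating; filling gaps and censoring after the last entry does not. Both are consistent with the text.

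A reader might also infer that the main and subtype tables follow different rules. The documents do not show this. The main title is silent, footnote [1] is not given, and SAP 4.3.4 and 6.2.2 apply to both tables. The SAP revision history records a change to LOCF, so the subtype title may be a leftover, though the SAP does not say so. Only the possibility of different classification stands.

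The visit schedule is a good answer on size. Protocol 10.2.2.3 to 10.2.2.5 have each symptom rated and entered in the diary on Days 3, 7 and 14, and 10.2.2.6 does so at early withdrawal where possible. Only a telephone Day 14 contact omits it. A later none/mild visit rating turns most early Grade 0 stops into gaps between observed ratings. The increases of 7% to 32% therefore cannot be read as expected effects: they need assumed shares and no usable visit ratings.

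Finally, the stakes are modest. The primary endpoints are safety, no hypothesis is tested, and the secondary endpoints are unranked.

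**Conclusion.** The concern holds as a gap in the SAP's rule. LOCF as written has no end point and can turn one final mild rating into 21.5 h of alleviation, while the neighboring censoring rule would leave the same child without an event. No precedence is stated, only one of two linked tables names a rule, and the sensitivity analyses meant to test the choice are not specified anywhere.

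The number of children affected cannot be computed, because the documents give no rate of missing diary entries. It is probably small provided visit ratings are used. In the illustration, Day 3 ratings alone cut the largest shift from 9.6 h (40.1 − 30.5) to 1.1 h (31.6 − 30.5), and adding Day 7 removes it. That rests on exponential times, none/mild visit ratings and every affected child attending. A child who misses those visits, or withdraws early, remains ambiguous. The point should be settled before analysis, but it does not threaten the trial's primary safety conclusions.

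**What to change.** In SAP 4.3.4, replace the two sentences with one rule:

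- Use all symptom ratings, from the diary and from visits.
- Apply LOCF only between two observed ratings, never after the last.
- Censor at the last observed rating any subject with less than 21.5 h at none or mild, including every subject who withdraws.
- As one stated exception to the 21.5 h requirement, count a subject who remains in the study and stops the diary as instructed at all-Grade 0 as alleviated from the start of that none/mild spell. This departs from the definition in Protocol 13.8.2, so list it in SAP section 7.

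Apply the rule to Tables 14.2.2.1.1.1 and 14.2.2.1.2.1 and their figures, and align the subtype title. Replace the pointer to 6.2.2.1 with a named sensitivity analysis that censors with neither imputation nor the Grade 0 exception. It would also show how much depends on filled gaps followed by relapse, as in the fourth diary above.

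The cost is SAP wording, one table title and one additional analysis. No new data are needed.
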